7.7.2.3 Continuous outcomes

Change from baseline for the continuous outcomes include:

- Change from baseline in SES-CD score at Week 16 and Week 52.
- Change from baseline in indices of health outcomes (Inflammatory Bowel Disease Questionnaire [IBDQ], Work Productivity and Activity Impairment Questionnaire for Crohn's Disease [WPAI-CD]) at post-baseline time points.
- Change from baseline in markers of inflammation (e.g. CRP, interleukins, cytokines, fecal calprotectin) at post-baseline time points.

Change from baseline in continuous outcomes will be analyzed by fitting fixed effects linear models to the data. An initial model with terms for treatment, country, baseline, and baseline by treatment interaction will be fitted. The interaction term will be tested at a 0.10 level. A non-significant interaction will result in dropping the term from the model in subsequent analyses. If the final model involves heterogeneous slopes, then the analysis will include overall plots of baseline versus change from baseline by treatment groups, and plots of the estimated regression lines.

Treatment differences will be estimated and tested at 25th, 50th and 75th percentiles of the baseline value.

The Work Productivity and Activity Impairment Questionnaire: Crohn's disease (WPAI: CD) is an instrument with 6 questions that will be used to assess the effect of CD on subjects' work habits.

WPAI: CD outcomes are expressed as impairment percentages, with higher numbers indicating greater impairment and less productivity, i.e., worse outcomes. The four WPAI: CD outcome scores are computed as follows:

- % work time missed due to CD = $100 \times Q2 / (Q2 + Q4)$
- % impairment while working due to CD = $100 \times Q5 / 10$
- % overall work impairment = $100 \times [Q2 / (Q2 + Q4) + (1 - Q2 / (Q2 + Q4)) \times (Q5 / 10)]$

- % activity impairment due to CD = $100 * Q6/10$

The IBDQ Global Score is the sum of 32 responses, each ranging from 1 to 7, thus the Global Score ranges from 32 to 224; a higher score indicating a better quality of life.

7.7.2.4 Time to event

Time to event related endpoints include:

- Time to clinical remission based on abdominal pain and liquid stool components of the co-primary endpoints.
- Time to clinical remission based on CDAI < 150.
- Time to loss of CDAI response defined by a CDAI score of 150 points during the Long Term Treatment Phase.

Time to event data (for example, time to clinical remission) will be analyzed by Kaplan-Meier analysis (PROC LIEFTTEST in SAS/STAT) stratified by country.

If the primary efficacy endpoints are not statistically significant, descriptive analysis will be performed for all secondary efficacy endpoints.

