#### **4.5 Premature Subject Discontinuation**

Subjects will be encouraged to complete the study; however, they may voluntarily withdraw at any time. Subjects withdrawn from the study will not be replaced.

A subject may be discontinued from study drug treatment and/or the study for the following reasons:

- Occurrence of an AE and/or SAE, which suggests an unacceptable risk to the subject, in the judgment of the investigator, including worsening of the disease under study.
- Pregnancy (see Section 7.7 for further details).
- Subject request to withdraw.
- Sponsor decision to terminate the study.

For all cases of premature withdrawal from the study listed above or any other, the investigator must provide the reason for discontinuation on the appropriate CRF page. *The investigator should make every attempt to obtain End of Treatment and End of Study assessments, including ileocolonoscopy.*

If treatment with investigational study drug has been prematurely discontinued, the End of Treatment assessments will be completed, and an attempt should be made to have the subject followed for 14 days after last administration of study drug to perform the End of Study assessments.

If a subject prematurely discontinues treatment with investigational drug at any time due to an AE or SAE, the End of Treatment assessments will be completed, and an attempt should be made to have the subject followed at least 14 days to perform the End of Study assessments, or until resolution or stabilization of the condition resulting in withdrawal has been confirmed.

The Investigator may discontinue individual subjects from the study at any time during the study. The investigator must provide the reason for discontinuation on the appropriate CRF page.

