**Confidential**

---

An additional consideration for sample size determination is the application of an inflation factor of 20% to account for drop-out rates during the Induction and Long Term Treatment Phases of the study. This consideration suggested that 330 subjects per treatment group would be required at study entry.

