7.10 Statistical and analytical issues

7.10.1 Handling of Dropouts or Missing Data

Missing data will be handled using the Worst-Case analysis method for the primary and key secondary endpoints. In the Worst-Case analysis, subjects with fewer than 4 days of diary data in a given week will be considered non-responders for that week. Additionally, subjects with missing SES-CD data will be classified non-responder for that measure in that week.

The following three sensitivity analyses will be conducted to address the impact of missing data on the primary and key secondary endpoints:

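### Time to clinical remission is analysed by Kaplan-Meier with no event or censoring rule; by default, withdrawals for worsening or adverse events are censored and the curves overstate the proportion who remit

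*SAP*

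**What the plan says.** SAP 7.7.2.4 lists "Time to clinical remission based on abdominal pain and liquid stool components of the co-primary endpoints" and time to CDAI below 150, and gives the method for both as "Time to event data (for example, time to clinical remission) will be analyzed by Kaplan-Meier analysis", run in the SAS lifetest procedure and stratified by country. Protocol 8.6.2 gives the same method. Neither states when the event is dated, who is censored and when, or what happens on withdrawal, rescue, surgery, death or early study closure. The section ends: "If the primary efficacy endpoints are not statistically significant, descriptive analysis will be performed for all secondary efficacy endpoints".

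Elsewhere the plan does say who counts as a failure:

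- SAP 7.7.1.1 and 7.7.1.2 count subjects who start rescue medication or have surgery for Crohn's disease as treatment failures from that date.
- SAP 7.7.2.1 sends the binary secondary endpoints to the primary method.
- SAP 7.10.1 applies a worst-case rule to the primary and key secondary endpoints: "subjects with fewer than 4 days of diary data in a given week will be considered non-responders for that week".

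None of these is extended to 7.7.2.4, and SAP section 8 does not mention the matter.

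Protocol 4.5 allows study drug or the study to be stopped for an adverse event that poses an unacceptable risk "in the judgment of the investigator, including worsening of the disease under study". End of Treatment assessments and about 14 days of follow-up come next. Protocol 4.3.2 keeps rescued subjects in the study as treatment failures. SAP 7.3 states that both studies will be terminated early.

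**The concern.** A Kaplan-Meier analysis needs either an event or a censoring time for each subject. A subject who leaves before remission has no event, so unless the plan says otherwise the subject is censored at the last assessment. Censoring assumes that the subject would later have remitted at the same rate as those still followed. That is hard to defend for someone who left because the disease worsened, and after the short follow-up no on-study remission can be observed.

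Three things follow. First, one minus Kaplan-Meier is no longer the proportion of treated subjects who reach remission. Secondly, the plan handles the same person in two ways: a subject withdrawn at Week 8 has no diary data before Week 16 and is a non-responder in the co-primary symptom analysis, but drops out of the risk set here. Thirdly, nothing stops a remission reached after rescue from counting as an event, although the SAP's own rule for the co-primary endpoints calls that subject a failure.

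Early closure makes a rule more necessary. Unwritten handling would mix harmless administrative censoring with outcome-related withdrawal.

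**Working it through.** **The plan's own figure.** The documents give no number for the time-to-event endpoints. The nearest is Protocol 8.2: 40% against 55%, about 240 per group, at least 90% power. With two-sided alpha 0.05 and pooled variance under the null:

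n = [1.960·√(2·0.475·0.525) + 1.282·√(0.40·0.60 + 0.55·0.45)]² / 0.15² = 231 per group, or 244 with continuity correction. Power at 240 is 91.1%. The stated figure reproduces.

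**Inputs for the illustration.**

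- r, the proportion seen to remit by Week 52: 40% placebo and 55% Rifaximin DR. These are the Protocol 8.2 Week 16 rates, borrowed here as cumulative first-remission rates. That is an assumption.
- d, the proportion withdrawn before remission for outcome-related reasons: assumed. Protocol 8.2 gives only an "inflation factor of 20% to account for drop-out rates during the Induction and Long Term Treatment Phases", not split by arm, reason or remission status. The range used is 5% to 36%. The upper end is 20% lost in each phase, 1 − 0.8 × 0.8 = 36%. The entry size is consistent with that compounding (210 / 0.64 = 328, against 330), but the documents do not state it.

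**Formula.** With constant hazards λ (remission) and μ (withdrawal) over follow-up T, r + d = 1 − exp[−(λ+μ)T] and r/(r+d) = λ/(λ+μ). Censoring the withdrawals gives

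1 − KM = 1 − exp(−λT) = 1 − (1 − r − d)^(r/(r+d)).

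With withdrawal as a competing failure, cumulative incidence is r itself.

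**At d = 20%.**

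- Placebo: 1 − 0.40^(0.40/0.60) = 45.7%, against 40%.
- Rifaximin DR: 1 − 0.25^(0.55/0.75) = 63.8%, against 55%.

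**Equal withdrawal in both arms (true difference 15.0 points).**

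| d | Placebo 1−KM | Excess | Rifaximin DR 1−KM | Excess | Difference |
|---|---|---|---|---|---|
| 5% | 41.2% | 1.2 | 56.8% | 1.8 | 15.6 |
| 10% | 42.6% | 2.6 | 58.9% | 3.9 | 16.3 |
| 20% | 45.7% | 5.7 | 63.8% | 8.8 | 18.1 |
| 36% | 52.8% | 12.8 | 76.7% | 21.7 | 23.9 |

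The last row is an upper bound: it needs 36 of the 45 non-remitters per 100 on Rifaximin DR (80%) to withdraw.

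**Unequal withdrawal (differences from unrounded values).**

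- 25% placebo, 15% Rifaximin DR: 47.6% and 61.2%, difference 13.6 points.
- 15% placebo, 25% Rifaximin DR: 44.1% and 66.9%, difference 22.9 points.

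**Check on the visit schedule.** A simulation of 200,000 subjects per scenario, with remission detected only at the scheduled visits and d = 20%, gives 46.2% and 64.2% with withdrawals censored. Holding the same subjects as non-remitters to Week 52 gives 40.1% and 55.0%.

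**The case against.** The strongest reply is that the SAP never says these subjects are censored. That is correct: the text leaves the rule open, and censoring is an inference from ordinary Kaplan-Meier practice. But holding a withdrawn subject as a non-remitter needs an instruction that the SAP lacks, so the method run as written produces the inflated curve.

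A reader might also infer a numerical conflict with the binary symptom endpoint, since the curves would lie above the Week 16 and Week 52 rates. The documents do not support that. The binary endpoints are status in the seven days before a fixed visit, while time to remission presumably counts first remission. A subject who remits at Week 8 and relapses is an event in one and a non-responder in the other, so the curve can be higher with no withdrawals at all. What stands is that the same withdrawn subject is handled differently.

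It can further be said that Kaplan-Meier and cumulative incidence answer different questions, and that counting every adverse-event withdrawal as a failure is a choice. That is fair. But the plan already makes that kind of choice for its other efficacy endpoints, and gives no reason to depart from it here.

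Finally, the consequence is small. These are items 12 and 13 of 15 in the ordered list of Protocol 2.2.3, and no primary or key secondary claim rests on them. This stands, and it limits the weight of the point. It does not remove it: if the primary endpoints fail, the curves are reported descriptively, and their level is then what readers will take away.

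**Conclusion.** The point holds as an unspecified rule whose default reading overstates remission. Under the stated assumptions (constant hazards, 40% and 55% remitting, equal outcome-related withdrawal in both arms) the overstatement is about 1 to 13 points on placebo and 2 to 22 points on Rifaximin DR for 5% to 36% withdrawn. At 20% it is 5.7 and 8.8 points.

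Two stronger conclusions are not supported. One is that the treatment effect is biased in a known direction: the difference rises or falls with withdrawal by arm, which is not given. The other is that the distortion is very large. If Week 52 remission on Rifaximin DR were assumed to be 62% with 36% withdrawn before remission, 36 of 38 non-remitters per 100 (95%) would have to withdraw. Nothing in the documents points to that, and Protocol 4.3.2 expects rescued subjects to stay.

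Because both studies close early, actual numbers and follow-up will differ from 330 per arm over 52 weeks, so precision and power for these endpoints cannot be sized from the documents. The change should be made, but its reach is limited to lower-order secondary endpoints.

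**What to change.** In SAP 7.7.2.4, for both time-to-remission endpoints:

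- Define the event and its date, for example the first visit at which the criterion is met.
- Treat as competing failures, if they occur before remission: withdrawal for worsening disease, lack of efficacy or an adverse event; death; and, in line with the SAP's own rule in 7.7.1.1, rescue medication or surgery for Crohn's disease.
- Report cumulative incidence by arm, compared with Gray's test stratified by country. Alternatively, hold these subjects as non-remitters to their own potential end of follow-up, the earlier of Week 52 and study closure. Holding everyone to Day 364 would be wrong, because some subjects could not have been followed that long.
- Censor administratively at study closure.
- Examine withdrawals for other reasons, such as subject request, in a sensitivity analysis.

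The cost is a paragraph of SAP text, withdrawal reasons mapped from the CRF, and the EVENTCODE option in PROC LIFETEST. The programmer should confirm that the installed release supports it, since SAP 7.1 allows version 9.3 or greater. The downside is that the reported remission curves will be lower.

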#### **8.7.5      Multiple Comparisons/Multiplicity**

The study has a single primary endpoint as the primary hypothesis, therefore no multiplicity adjustment is needed to the overall significance level of 0.05. Additionally, the clinical trial will be providing data for two separate indications (induction and long term treatment) with each indication having its own separate endpoint. On that basis, no multiplicity adjustment is needed to the overall significance level of 0.05 per indication because conclusions will be reached independently for induction and separately for long term treatment.

The complete evaluation of clinical efficacy in this study requires the study of multiple key secondary efficacy variables collected at numerous time points. It is therefore necessary to properly and sensitively control the probability of making erroneous conclusions based solely upon compounding the likelihood of a type I error. The issue of multiplicity of secondary measurements will be handled by statistical testing of these outcomes in a hierarchical fashion. The order of secondary endpoints for the Induction and Long Term Treatment Phases are described in Sections 2.2.2 and 2.2.3. Significance tests will be conducted until a non-significant p-value is found ( $p > 0.05$ ). Once a non-significant p-value occurred, all subsequent significance tests will be considered exploratory in nature.

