7.3 Sample Size

For sample size justification, reference corresponding study protocols.

Originally planned sample sizes per arm for each of the studies are listed below:

Study	Treatment A: Rifaximin DR Tablets 800 mg BID	Treatment B: Placebo BID
RECD3125	330	330
RECD3126	330	330

Both studies will be terminated early therefore the actual sample size may vary.

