7.7 Efficacy Analysis

The phrases 'statistical analysis' or 'analysis' will be used to mean inferential analysis (such as performing tests of significance, reporting p-values and confidence intervals). When no inferential analysis will be performed, the phrases 'descriptive analysis' or 'descriptive statistics' will be used (for instance, producing summary tables of means, standard deviations, percentages of responders). All efficacy analyses will be conducted on ITT population. All efficacy analyses will adjust for country.

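### If the co-primaries are not both significant, the SAP reduces the secondary efficacy endpoints of 4.3 to descriptive summaries, with no adjusted treatment difference and no confidence interval

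*SAP*

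**What the plan says.** SAP 7.7 fixes the vocabulary. The word analysis is "used to mean inferential analysis (such as performing tests of significance, reporting p-values and confidence intervals". The alternative is defined by exclusion: "When no inferential analysis will be performed, the phrases 'descriptive analysis' or 'descriptive statistics' will be used". The examples given for it are "producing summary tables of means, standard deviations, percentages of responders".

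SAP 7.7.2 then plans inference for the endpoints listed in 4.3. Binary endpoints follow the primary method, a country-stratified CMH test. Continuous endpoints get a linear model with treatment, country and baseline, for which 7.7.2.3 says "Treatment differences will be estimated and tested at 25th, 50th and 75th percentiles of the baseline value". Time-to-event endpoints get a country-stratified Kaplan-Meier analysis. The last sentence of 7.7.2.4 makes this conditional: "If the primary efficacy endpoints are not statistically significant, descriptive analysis will be performed for all secondary efficacy endpoints".

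SAP 7.3 gives the setting: "Both studies will be terminated early therefore the actual sample size may vary".

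Protocol 8.7.5 has a different rule. It tests secondary endpoints in a fixed order, and "Once a non-significant p-value occurred, all subsequent significance tests will be considered exploratory in nature". SAP 7.11 omits that ordered procedure. SAP Section 8, which lists planned evaluations that will not be performed, mentions neither the omission nor the switch to description.

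**The concern.** Withholding significance claims once the primary hypothesis has failed is normal practice. The SAP sentence goes further, because descriptive is a defined term. Read with 7.7, it removes interval estimates and model-based differences along with the p-values.

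This matters more in a trial that stops early. A co-primary pair can miss significance because the drug does little or because too few subjects were enrolled. An adjusted difference with an interval helps to separate the two, and per-arm means or percentages alone do not. The loss is clearest for the baseline- and country-adjusted mean differences in SES-CD, IBDQ, WPAI-CD and inflammatory markers, and for country-adjusted comparisons of the binary endpoints.

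**Working it through.** **Step 1: what survives the rule.** SAP 7.7 is the only place in the SAP that mentions confidence intervals, and it puts them on the inferential side. The differences planned in 7.7.2.3 and the stratified comparisons in 7.7.2.1 are inferential in that sense. The only explicit interval for an efficacy outcome in the protocol is the 95% CI on least squares means from the mixed model (Protocol 8.6.2), and SAP Section 8 drops that model. SAP 7.1 still supplies n, mean, SD, median, minimum and maximum, and counts with percentages. The per-arm summaries remain; adjusted differences and intervals do not.

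**Step 2: reproduce the plan's power.** Inputs are 40% versus 55% and about 240 per group with at least 90% power for each co-primary (Protocol 8.2), and p < 0.05 with a two-sided alternative (SAP 7.7.1.1). For n per arm:

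- SE0 = sqrt(2 × 0.475 × 0.525 / n)
- SE1 = sqrt((0.40 × 0.60 + 0.55 × 0.45) / n) = sqrt(0.4875 / n)
- power = Φ((0.15 − 1.96 × SE0) / SE1)

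At n = 240, SE0 = 0.0456 and SE1 = 0.0451, so power = Φ(1.35) = 91.1%. This agrees with the stated figure. If the two tests are independent, both succeed with probability 0.911² = 83%, against about 80% in the protocol.

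**Step 3: how often the rule applies.** The same formula is used at smaller sizes. Joint power is Φ₂(a, a; ρ), where a is the argument of Φ above and ρ, from 0 to 0.6, is the assumed correlation between the two test statistics. At ρ = 0 it is the square of the single power. The half-width is 1.96 × SE1.

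| n per arm (assumed) | each significant | both significant | pair fails | 95% CI half-width at 40% vs 55% |
|---|---|---|---|---|
| 150 | 74% | 55-62% | 38-45% | 11.2 points |
| 100 | 57% | 32-42% | 58-68% | 13.7 points |
| 50 | 32% | 10-19% | 81-90% | 19.4 points |

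**Step 4: where failure becomes likelier than success.** At 140 per arm, single power is 71.2% and 0.712² = 50.7%. At 135 it is 69.6% and 0.696² = 48.5%. With independent tests the crossover is just under 140 per arm. Positive correlation moves it lower.

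**Step 5: what an interval would show.** At 50 per arm, an observed difference of 15 points has a 95% interval of 15 ± 19.4, or −4.4 to 34.4 points. The interval shows that such a result is compatible with no effect and also with a large one.

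**The case against.** Several points on the other side stand.

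- **The rule is only part of the cause.** Even after success, the SAP names no interval for most secondary differences. Binary endpoints get a CMH test, durable response a Kolmogorov-Smirnov test, and time-to-event endpoints a Kaplan-Meier analysis without a stated contrast. Descriptive output would not bar Kaplan-Meier estimates. This is right, and it is why the fix also covers the CMH-tested endpoints. But a successful trial keeps the word analysis, which by definition includes intervals, whereas a failed one loses it.
- **Every secondary endpoint is affected.** A reader might infer this, but the documents do not support it. The Week 52 key co-secondaries have their own CMH tests in SAP 7.7.1.2, SAP 7.11 treats the long-term conclusion as independent of induction, and the rule's wording matches the heading of 4.3, not 4.2. Their status is unclear.
- **No precision is reported at all.** This is also too strong. The examples in 7.7 are only examples, and SAP 7.1 supplies n, SDs and counts, from which crude intervals can be rebuilt and the two studies crudely pooled. Country- and baseline-adjusted results cannot be rebuilt.
- **The terms are used loosely.** Protocol 8.5 lists 95% confidence intervals among descriptive measures of baseline comparability. SAP 7.6.2.2 does not carry this over, and it concerns baseline data.
- **The protocol promised no intervals either.** Section 8.7.5 only relabels tests. That is true. The departure is that planned comparisons are withdrawn instead of relabelled.
- **Extra analyses are allowed.** SAP 7.1 permits supplementary analyses after lock. They would then be chosen once the result is known.
- **Description is defensible for an abbreviated report.** It is, and it inflates no error rate. Nominal intervals spend no alpha either.

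**Conclusion.** The point holds for the secondary efficacy endpoints of SAP 4.3. If the co-primaries are not both significant, the SAP as written reports neither a country- or baseline-adjusted treatment difference nor a confidence interval for them, and SAP Section 8 does not declare this departure from Protocol 8.7.5. Whether the key co-secondaries are also affected cannot be settled from the text.

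The size depends on the final enrolment, which the documents do not give. A reader might infer that failure is the likely outcome of stopping early, but at the planned effect that is so only below about 140 per arm with independent tests. At 150 per arm success is still likelier. The failure rates assume the planned 40% versus 55% for each co-primary and a correlation of 0 to 0.6 between the tests. I take the trigger to mean not both significant, in line with the claim rule in 7.7.1.1. The half-widths of about 11, 14 and 19 points use the co-primary rates and are illustrative only, since the documents give no expected rates for the endpoints in 4.3.

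The primary conclusion and its Type I error are unaffected. What suffers is how informative a truncated trial's report can be.

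**What to change.** Replace the last sentence of SAP 7.7.2.4, and move it to the start of 7.7.2 because it governs all of that section. Suggested wording: *If the co-primary endpoints are not both significant, no secondary hypothesis test will be claimed. Treatment differences with nominal 95% confidence intervals will still be reported and labelled exploratory: a country-adjusted risk difference for binary endpoints, the adjusted mean difference from the model in 7.7.2.3 for continuous endpoints, and Kaplan-Meier estimates with intervals for time-to-event endpoints.*

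In addition:

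- State whether the rule covers the two Week 52 key co-secondary endpoints.
- Report a country-adjusted risk difference with its confidence interval beside the CMH p-value of each co-primary and key co-secondary endpoint, since 7.7.1.1 and 7.7.1.2 specify only a test.
- List the departure from Protocol 8.7.5 in SAP Section 8.

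The cost is SAP wording and a few more output columns. The country strata and the continuous-outcome model are already specified, no new data are needed, and no alpha is spent. The downside is a set of intervals not adjusted for multiplicity, which must be labelled as not supporting claims.
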